5.4.3.3 Congenital Anomalies/Birth Defects

Any congenital anomaly/birth defect in a child born to a female subject or a female partner of a male subject exposed to study drug should be classified as a serious adverse event, recorded on the Adverse Event eCRF, and reported to the Sponsor immediately (i.e., no more than 24 hours after learning of the event; see Section 5.4.2).

5.5 FOLLOW-UP OF SUBJECTS AFTER ADVERSE EVENTS

5.5.1 Investigator Follow-Up

The investigator should follow each adverse event until the event has resolved to baseline grade or better, the event is assessed as stable by the investigator, the subject is lost to follow-up, or the subject withdraws consent. Every effort should be made to follow all serious adverse events considered to be related to study drug or trial-related procedures until a final outcome can be reported.

During the study period, resolution of adverse events (with dates) should be documented on the Adverse Event eCRF and in the subject's medical record to facilitate source data verification. If, after follow-up, return to baseline status or stabilization cannot be established, an explanation should be recorded on the Adverse Event eCRF.

All pregnancies reported during the study should be followed until pregnancy outcome and reported according to the instructions provided in Section 5.4.3.

5.5.2 Sponsor Follow-Up

For serious adverse events, adverse events of special interest, and pregnancies, the Sponsor or a designee may follow up by telephone, fax, email, and/or a monitoring visit to obtain additional case details and outcome information (e.g., from hospital discharge summaries, consultant reports, autopsy reports) in order to perform an independent medical assessment of the reported case.

5.6 ADVERSE EVENTS THAT OCCUR AFTER THE ADVERSE EVENT REPORTING PERIOD

The investigator is not required to actively monitor subjects for adverse events after the end of the adverse event reporting period (defined as 6 weeks after the last dose of study drug). However, the Sponsor should be notified if the investigator becomes aware

of any serious adverse event that occurs after the end of the adverse event reporting period if the event is believed to be related to prior study drug treatment.

The investigator should report these events directly to the Sponsor or its designee, either by faxing or by scanning and emailing the paper Clinical Trial Serious Adverse Event/Adverse Event of Special Interest Reporting Form using the fax number or email address provided to investigators.

5.7 EXPEDITED REPORTING TO HEALTH AUTHORITIES, INVESTIGATORS, INSTITUTIONAL REVIEW BOARDS, AND ETHICS COMMITTEES

The Sponsor will promptly evaluate all serious adverse events and adverse events of special interest against cumulative product experience to identify and expeditiously communicate possible new safety findings to investigators, IRBs, ECs, and applicable health authorities based on applicable legislation.

Independent from the causality assessment, the following serious adverse events and non-serious adverse events of special interest will be reported to the FDA on an expedited basis: death, arrhythmia, syncope, dyspnea, palpitations, and chest pain.

To determine reporting requirements for single adverse event cases, the Sponsor will assess the expectedness of these events to balovaptan using the following reference document:

- Balovaptan Investigator's Brochure

The Sponsor will compare the severity of each event and the cumulative event frequency reported for the study with the severity and frequency reported in the applicable reference document.

Reporting requirements will also be based on the investigator's assessment of causality and seriousness, with allowance for upgrading by the Sponsor as needed. An iDMC will monitor the incidence of these events during the study. An aggregate report of any clinically relevant imbalances that do not favor the test product will be submitted to health authorities.

6. STATISTICAL CONSIDERATIONS AND ANALYSIS PLAN

Database lock to enable the analysis of the 24-week, placebo-controlled phase of the study will occur once all subjects have either completed the 24-week assessment or withdrawn from the study early, and all data required for analysis have been cleaned and verified. After database lock, treatment assignments will be unblinded to the Sponsor.

The final analysis of the 24-week placebo-controlled period will be performed after database lock. The final analysis of all data collected in the study, including the open-label extension, will occur after all subjects have completed the study.

Details of the planned statistical analyses mentioned below in this section will be fully specified in the Statistical Analysis Plan, which will be finalized prior to the locking the study database and unblinding the study.

6.1 ANALYSIS POPULATIONS

6.1.1 Safety Population

The safety population will consist of all subjects who receive any study treatment. Randomized subjects who receive incorrect therapy from that intended will be summarized in the group according to their planned randomized treatment.

The safety population will be the primary population for all analyses of safety data.

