3.1.1.4 Open-Label Extension Period

All subjects who complete the 24-week double-blind treatment period are eligible for participation in the open-label extension period of the study. Subjects who are not willing to participate in the open-label extension period of the study will complete the safety follow-up visits. Subject treatment allocation during the double-blind treatment period will not be unblinded regardless of a subject's participation in the open-label extension period.

The 2-year (104-week) duration of the open-label extension period serves to evaluate the long-term safety, tolerability, and efficacy of balovaptan treatment in subjects with ASD. All subjects will receive 10 mg of oral balovaptan QD. For the schedule of activities to be performed during the open-label extension, see [Appendix 3](#).

After the predose assessments have been completed, each subject will receive an oral dose of balovaptan. After completion of the postdose evaluations and following a medical check-up by a physician, the subject will be discharged from the study center. If the visit is split over 2 days, study drug (balovaptan) must be administered QD after the completion of all assessments.

Checks for signs and symptoms of infection will be conducted according to the schedule of activities.

As a general rule, the test sequence for all assessments should remain the same for a given subject as previously established at screening and baseline. At all visits, PRO assessments should be completed prior to any other assessments. All assessments must be performed before administration of study drug.

For informant-based assessments, the following order of assessments will be followed:

- The Vineland-II will be the first informant-based assessment with a subject's study partner.
- For all other informant-based assessments, there is no restriction in the order, a sequence established at screening and baseline should remain the same for a given subject; however, subject assessments should be prioritized. The suggested sequence is provided in [Table 3](#). It will be possible for assessments (e.g., the Vineland-II interview and subject assessments) to be conducted in parallel if the site has sufficient qualified raters available.

The last assessments to be completed are the Clinical Global Impression scales.

At visits when blood samples are obtained, the order of assessments should be as follows:

- 12-Lead ECGs
- Vital signs
- Physical and neurologic examinations

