4.2 METHOD OF TREATMENT ASSIGNMENT AND BLINDING

Approximately 350 subjects will be randomized to receive either placebo or 10 mg of oral balovaptan QD in a 1:1 ratio. An independent interactive voice or web-based response system (IxRS) provider will conduct randomization and hold the treatment assignment code. Randomization will be stratified by a subject's baseline Vineland-II 2DC score (<60 vs. ≥60), sex (male vs. female), region (North America vs. ROW), and age (<25 years vs. ≥25 years).

There will be no replacement of subjects should a subject's treatment be discontinued for any reason.

Study site personnel and subjects will be blinded to treatment assignment during the study. The Sponsor and its agents will also be blinded to treatment assignment, with the exception of individuals who require access to subject treatment assignments to fulfill their job roles during a clinical trial.

If unblinding is necessary for a medical emergency (e.g., in the case of a serious adverse event for which subject management might be affected by knowledge of treatment assignment), the investigator will be able to break the treatment code by contacting the IxRS. The investigator is not required to contact the Medical Monitor prior to breaking the treatment code; however, the treatment code should not be broken except in emergency situations. If unblinding occurs, subjects should not continue receiving study drug and should proceed to the end-of-treatment visit and subsequently safety follow-up.

If the investigator wants to know the identity of the study drug for any reason other than a medical emergency, he or she should contact the Medical Monitor directly. The investigator should document and provide an explanation for any non-emergency unblinding. The investigator will be able to break the treatment code by contacting the IxRS.

Whenever disclosure of the identity of the study drug is necessary, adequate procedures will be put in place to ensure integrity of the data. Any unblinding at the investigational site will be documented in the study report with the date, the reason for identifying the drug, and the name of all person(s) who were unblinded.

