6.1.2 Intent-to-Treat Population

The ITT population will consist of all subjects who receive any study treatment. Randomized subjects who receive incorrect therapy from that intended will be summarized in the group according to their planned randomized treatment.

The ITT population will be the primary population for all analyses of primary and secondary efficacy variables.

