6.6 SAFETY DATA ANALYSIS

All verbatim adverse event terms will be mapped to MedDRA thesaurus terms, and adverse event severity will be graded according to [Table 4](#). All safety data will be reported in individual listings and summarized by treatment for each assessment time using descriptive statistics. Data collected during the follow-up period (i.e., after discontinuation of study treatment) will be summarized separately from the data collected during the treatment period.

The incidence of adverse events will be summarized on the basis of body systems and dictionary preferred terms. The incidence of adverse events by severity and relationship to study drug and incidence of marked abnormal laboratory test results will be provided. Laboratory tests, ECG, and vital signs data will be summarized by descriptive statistics both as original value as well as the change from baseline.

The iDMC will review safety data throughout the study. Analyses required for the iDMC data review will be performed as described in the iDMC Charter.

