6.7 PHARMACOKINETIC AND PHARMACODYNAMIC ANALYSES

A population-PK analysis will be performed to describe the pharmacokinetics of balovaptan in subjects with ASD and to assess the influence of covariates of interest on the PK parameters. Non-linear mixed effects modeling (using the software, NONMEM) will be used to analyze the concentration–time data of balovaptan. The starting model will be a model developed based on data from previous Phase I/II studies (Roche Report No. 1081347). The data collected in this study may be pooled with data collected in previous studies as appropriate to inform the population-PK model. Population and individual primary PK parameters (e.g., clearances and volumes) will be estimated. Secondary PK parameters such as AUC and maximum plasma concentration will be derived from the individual post-hoc predictions. In addition, measured plasma concentrations of M2 (as applicable) and M3 metabolites will be summarized by timepoint and the relationship of parent and metabolite, as well as the influence of covariates of interest may be explored graphically. Plasma concentrations of balovaptan, its metabolites M2 (RO7045402) as applicable, and M3 (RO5273004) will be measured using a specific and validated liquid chromatography tandem mass spectrometry method.

Graphical exploration of the relationship between balovaptan exposure and the Vineland-II 2DC score and other selected clinical efficacy and safety endpoints will be performed. If indicated by such exploration, more formal analyses of the exposure–response relationship will be performed using pharmacometric modeling methods.

Details of the PK and pharmacodynamic analyses will be described in a Modeling and Simulation Analysis Plan. The results will be reported in a document separate from the Clinical Study Report.

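### Section 6.1.1 tabulates wrongly treated subjects under planned treatment for safety, and the documents name no summary by treatment received

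*Combined protocol and SAP*

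**What the plan says.** Section 6.1.1 takes every treated subject into the safety population and fixes the grouping of those given the wrong drug: "Randomized subjects who receive incorrect therapy from that intended will be summarized in the group according to their planned randomized treatment." It adds: "The safety population will be the primary population for all analyses of safety data."

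Section 6.1.2 repeats the grouping sentence word for word and uses the same membership: "The ITT population will consist of all subjects who receive any study treatment." The safety and ITT populations are therefore the same subjects in the same groups.

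Section 6.6 says: "All safety data will be reported in individual listings and summarized by treatment for each assessment time using descriptive statistics." It names no table by treatment received, and no other section does. For the data monitoring committee it says only: "Analyses required for the iDMC data review will be performed as described in the iDMC Charter."

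Wrong-drug errors are foreseen. Section 4.3.2 has incorrect administration noted on the Study Drug Administration eCRF. Section 5.3.5.11 counts a wrong drug as a medication error. It requires each adverse event associated with such an error to have its own Adverse Event eCRF page, with the medication-error box ticked.

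**The concern.** The safety objective is to compare 10 mg of balovaptan with placebo. Grouping by assignment suits efficacy, where it protects the randomized comparison. For safety, it counts a subject known to have taken the other drug under a drug that he or she did not take. In expectation this pulls the arms together and makes a real safety difference look smaller; in a single trial the counts can move either way.

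Common events would hardly be affected. Rare ones are different. Serious events in the Phase II study were isolated (Section 1.2.2.1 mentions sinus node dysfunction, syncope and rhabdomyolysis), and Section 5.7 singles out death, arrhythmia and syncope, among others, for expedited reporting. At such counts, one misplaced subject can change how a table reads.

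**Working it through.** **Inputs.**
- 175 subjects per arm (Section 6.2). The stated power reproduces: a difference of 4.0, SD 12.5 and two-sided 5% with 175 per arm give 84.9%, against 85% stated. The present point does not depend on it.
- Six double-blind supplies of 4 weeks each, dispensed at baseline and Weeks 4, 8, 12, 16 and 20 (Appendix 1).
- k wrongly treated subjects in one arm, each with j of the six supplies wrong. The documents give no error rate, so k and j are assumptions.
- Risk is taken as proportional to time on drug, and j as equal across the k subjects.

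**Present rule (grouped as planned).** The k subjects stay in their assigned arm, so the expected risk difference shrinks by (k/175) × (j/6). For whole-period errors (j=6) this is k/175:
- k=1: 1/175 = 0.6%
- k=5: 5/175 = 2.9%
- k=10: 10/175 = 5.7%

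**Majority rule (grouped by the treatment taken for most of the dosing time, ties as planned).** Subjects move only when j is 4 or more. The receiving group then has 175 + k subjects, and the shrinkage is [k/(175 + k)] × (6 − j)/6.

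| Wrong supplies j | Planned, k=1 | Majority, k=1 | Planned, k=10 | Majority, k=10 |
|---|---|---|---|---|
| 1 | 0.10% | 0.10% | 0.95% | 0.95% |
| 2 | 0.19% | 0.19% | 1.90% | 1.90% |
| 3 | 0.29% | 0.29% | 2.86% | 2.86% |
| 4 | 0.38% | 0.19% | 3.81% | 1.80% |
| 5 | 0.48% | 0.09% | 4.76% | 0.90% |
| 6 | 0.57% | 0% | 5.71% | 0% |

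In this model the majority rule never shrinks the difference more than the present rule. Both formulas are the same whether placebo subjects receive balovaptan or balovaptan subjects receive placebo.

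**An alternative not recommended.** Counting every mixed-exposure subject under balovaptan would apply the second formula at j=1. That gives (1/176) × (5/6) = 0.47% for k=1 and (10/185) × (5/6) = 4.5% for k=10, about five times the present rule.

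**Rare events.** Suppose three events occur, all in subjects taking balovaptan, and one of these subjects was assigned placebo.
- As planned: 2/175 = 1.1% against 1/175 = 0.6%.
- As received: 3/176 = 1.7% against 0/174 = 0%.

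If k placebo-assigned subjects take balovaptan throughout, the chance that at least one of three such events is misplaced is 1 − C(175,3)/C(175+k,3). This is 1.7% for k=1 and 15.4% for k=10. The latter requires 10 of 175 subjects (5.7%) to be on the wrong drug for the whole period.

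**The case against.** The strongest reply has four parts.

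**The Statistical Analysis Plan may add the table.** Section 6 leaves analysis details to a separate plan that is not in the document reviewed. Section 6.1.1 calls this population primary, so a supplementary as-treated table would not contradict it. This stands: a reader might infer that the trial will produce no safety table by treatment received, but the documents show only that they name none. The primary grouping is nevertheless stated outright, and a supplementary table would leave it unchanged.

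**Errors are unlikely.** Section 4.2 says: "An independent interactive voice or web-based response system (IxRS) provider will conduct randomization and hold the treatment assignment code." This also stands, and nothing in the documents suggests frequent misdispensing.

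**Safeguards exist.** Medication-error flags and individual listings let a reader trace single cases, and Section 6.7 adds: "Graphical exploration of the relationship between balovaptan exposure and the Vineland-II 2DC score and other selected clinical efficacy and safety endpoints will be performed." These help with interpretation, but none changes the counts by arm. The exposure graphs cover selected safety endpoints only.

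**Regrouping gives up the randomized comparison for the subjects moved.** This is true and is the price of the change. Grouping as planned is a stated choice and not an internal contradiction.

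Two further inferences should be resisted. A single wrong supply does not put a subject in the wrong group: the present rule already places that subject under the treatment mostly taken, and only an event during that supply is misplaced. Nor do the documents show that the monitoring committee's tables or the aggregate report in Section 5.7 are affected, since the Charter was not available.

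**Conclusion.** The point holds in a limited form. For the primary safety analyses, a subject recognised as having taken the other arm's drug for all or most of the double-blind period is tabulated under the wrong treatment, and on average this dilutes a safety difference. The expected loss is small: k/175 for whole-period errors, and less for partial ones, under the assumed k and risk proportional to time on drug. It would matter chiefly for rare or serious events. This does not threaten the trial, but it is worth correcting before unblinding because the correction is cheap and uses data already captured.

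A minor secondary point is that Section 6.1.2 gives the ITT name to a treated-only set. Few subjects are likely to be affected, since randomization and first dose both fall on Day 1.

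**What to change.** **Section 6.1.1.** Group the double-blind safety summaries by treatment actually received. Place subjects who received both treatments under the one taken for most of their double-blind dosing time, with ties under planned treatment. The limit to the double-blind period is needed because in the extension "All subjects will receive 10 mg of oral balovaptan QD."

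**Listing.** For mixed-exposure subjects, list adverse events by the treatment most recently taken at or before onset. This wording also covers events after the last dose, which Section 5.3.1 collects for 6 weeks. The listing can build on the existing medication-error flag and adds the events that the site did not link to the error.

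**Section 6.1.2 (secondary).** Define ITT as all randomized subjects, grouped as randomized.

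**Cost and limits.** The change takes two sentences in 6.1.1, one in 6.1.2 and one listing. Regrouped subjects leave their randomized group for safety. A wrong supply covering a minority of dosing time changes only the listing. Errors that are never recognised cannot be regrouped, and the required content of the Drug Dispensing Log in Section 4.3.3 is dates and quantities only. PK samples at Weeks 2, 8, 12, 20 and 24 fall in five of the six supply intervals (all but Weeks 12–16) and might reveal some errors, but the documents do not say whether placebo-arm samples are assayed.

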6.1.2 Intent-to-Treat Population

The ITT population will consist of all subjects who receive any study treatment. Randomized subjects who receive incorrect therapy from that intended will be summarized in the group according to their planned randomized treatment.

The ITT population will be the primary population for all analyses of primary and secondary efficacy variables.

6.2 DETERMINATION OF SAMPLE SIZE

The sample size of 350 randomized subjects (175 subjects per arm) provides 85% power to detect a difference in means between treatments in the change from baseline at Week 24 on the Vineland-II 2DC score of at least 4.0 points, assuming a two-sided 5% significance level and a standard deviation of about 12.5 points. A blinded interim analysis of the change in Vineland-II 2DC score from baseline may be performed by the Sponsor to allow an increase in the sample size if necessary to achieve appropriate study power.

6.3 SUMMARIES OF CONDUCT OF STUDY

The number of subjects who enroll, discontinue, or complete the study will be summarized by treatment group. Reasons for premature study withdrawal will be listed and summarized.

6.4 SUMMARIES OF TREATMENT GROUP COMPARABILITY

Demographic and baseline characteristics (including age, sex, WASI®-II IQ score, SRS-2 total *t*-score) will be summarized by treatment group using means, standard deviations, medians and ranges for continuous variables, and proportions for categorical variables, as appropriate. Summaries will be presented overall and by treatment.

6.5 EFFICACY ANALYSES

6.5.1 Primary Efficacy Endpoint

The primary efficacy endpoint is the change from baseline at Week 24 on the Vineland-II 2DC score, defined as the mean of the Communication domain standard score and the Socialization domain standard score.

